1.0 Study Rationale and Background

Axial rigidity is a cardinal motor feature of Parkinson's Disease (PD), characterized by stiffness in the trunk and spine. Unlike appendicular symptoms (such as tremor), axial symptoms often show limited response to standard dopaminergic medication (e.g., Levodopa) and contribute significantly to gait impairment, balance dysfunction (postural instability), and chronic pain.

This observational study investigated the utility of a novel robotic device, BackHug, to mechanically mobilize the thoracic and lumbar spine, evaluating the hypothesis that reducing axial stiffness improves systemic mobility and reduces symptom burden.

2.0 Study Objectives

Primary Objective: To observe whether the mechanical release of axial rigidity via robotic spinal mobilization correlates with measurable improvements in functional mobility.

Secondary Objectives: To observe whether the intervention correlates with:

- A reduction in chronic back pain intensity.
- An improvement in sleep quality.
- An improvement in functional lower limb strength.

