4.0 Eligibility Criteria

4.1 Inclusion Criteria

- Confirmed clinical diagnosis of Parkinson's Disease.
- Hoehn and Yahr Scale Stage 3 or below (indicating mild to moderate disability).
- Ability to walk independently for approximately 5 minutes (with or without walking poles; Zimmer frames excluded).
- Age 18 to 75 years.

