4.2 Exclusion Criteria

Participants were excluded if they presented with any absolute contraindication to mechanical spinal mobilization, including:

- **Bone Pathology:** History of spinal malignancy, active spinal infection (e.g., tuberculosis), severe congenital defects, metabolic bone disease (e.g., severe osteomalacia), or currently healing fractures/dislocations.
- **Inflammatory Conditions:** Severe Rheumatoid Arthritis or other inflammatory arthritides.
- **Neurological Conditions (Non-PD):** Spinal cord compression, spinal cord damage, Cauda Equina syndrome.
- **Vascular Risks:** History of aortic dysfunction (e.g., aneurysm), severe haemophilia, or unmanaged bleeding disorders.

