6.3 Pain Intensity (Secondary Outcome)

- **Metric:** Visual Analog Scale (VAS).

- **Scale:** 0 (No Pain) to 10 (Worst Possible Pain).
- **Timing:** Assessed longitudinally throughout the study.

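### The pain objective is chronic back pain, but entry requires no pain, the VAS has no stated site or recall window, and all completers are pooled, so the pooled VAS change does not answer it

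*Combined protocol and SAP*

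**What the plan says.** Section 2.0 gives the pain objective as "A reduction in chronic back pain intensity". The word chronic is not defined there or later.

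Section 4.1 has four inclusion criteria: "Confirmed clinical diagnosis of Parkinson's Disease", disease stage no higher than Hoehn and Yahr 3, "Ability to walk independently for approximately 5 minutes", and "Age 18 to 75 years". None concerns pain. Section 4.2 removes people with "any absolute contraindication to mechanical spinal mobilization", so someone with no pain remains eligible.

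Section 6.3 measures pain intensity on a VAS scored "0 (No Pain) to 10 (Worst Possible Pain"). It names no body site and no recall period.

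SAP section 7.2 defines one efficacy set: those who completed all four sessions and had both assessments. Section 7.3 adds an observed-case rule for each endpoint. Section 7.4.2 compares VAS scores at baseline and final in that set and expresses improvement as a percentage of the baseline score. It has no back-pain subset and no rule for a baseline of 0. Section 7.1 says the study should yield effect sizes and SDs good enough to power a later randomised trial.

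**The concern.** The objective names a symptom (back pain), a course (chronic) and, by implication, a population (people who have it). The endpoint and its analysis fix none of the three. A change in pain at another site can count as, or hide, a change in back pain. A participant who starts at 0 can only stay there or worsen.

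Two things are at stake. One is the secondary conclusion: if the plan is followed as written, a statement about chronic back pain would rest on a quantity that is not chronic back pain. The other is the planning value of the pilot: a mean and SD from a mixture of people with and without the symptom describe neither group.

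**Working it through.** **Step 1. Objective against endpoint (text only, no assumptions).**

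| Element | Objective (2.0) | What is measured and analysed |
|---|---|---|
| Site | Back | Not stated (6.3) |
| Course | Chronic, undefined | No recall window (6.3) |
| Population | People with that pain | No pain requirement (4.1, 4.2); all completers (7.2, 7.4.2) |

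The mismatch holds in every row.

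**Step 2. Is there a figure to reproduce?** Only N=16 (7.1), which was set by feasibility. The documents give no pain effect, no SD and no pain-free share, so everything below except the 1/baseline argument in step 5 rests on assumptions.

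**Step 3. Mean.** Let k of n=16 be pain-free with no change, q = k/16, and d the mean reduction in the others. The pooled mean is (1−q)d.
- k=4: q=0.25, mean 0.75d, 25% smaller.
- k=8: q=0.50, mean 0.50d, 50% smaller.

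These percentages do not depend on d.

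**Step 4. SD and standardised effect.** With SD s in those with back pain, the pooled SD is √[(1−q)s² + q(1−q)d²]. For assumed d=1.5 and s=2.0:
- k=0: mean 1.500, SD 2.000, effect 0.750.
- k=4: mean 1.125, SD √(3.000+0.422)=1.850, effect 0.608.
- k=8: mean 0.750, SD √(2.000+0.5625)=1.601, effect 0.469.

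The standardised effect over a range of d, with s=2.0:

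| d | k=0 | k=4 | k=8 |
|---|---|---|---|
| 1.0 | 0.500 | 0.420 | 0.333 |
| 1.5 | 0.750 | 0.608 | 0.469 |
| 2.0 | 1.000 | 0.775 | 0.577 |

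Required sample size goes roughly as 1/effect². At d=1.5, a later trial confined to chronic back pain but planned on the pooled figure would be too large by (0.750/0.608)² ≈ 1.5 times (k=4) or (0.750/0.469)² ≈ 2.6 times (k=8).

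**Step 5. Percentage improvement.** The formula in 7.4.2 divides by baseline, so it has no value for a participant at 0. (A percentage taken on group means would exist; the section does not say which is meant.) If 20% of eligible people were pain-free, the chance of at least one among 16 is 1 − 0.8¹⁶ = 0.972.

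**Step 6. Does restricting the set gain power?** Paired t-test, two-sided 5% (sidedness is not stated in the SAP), s=2.0, k fixed, pain-free change exactly 0. The all-16 column is by simulation (20,000 runs); the subset column uses the noncentral t.

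| d | k | All 16 | Subset (n=16−k) |
|---|---|---|---|
| 1.0 | 4 | 0.346 | 0.353 |
| 1.0 | 8 | 0.207 | 0.232 |
| 1.5 | 4 | 0.654 | 0.658 |
| 1.5 | 8 | 0.418 | 0.449 |
| 2.0 | 4 | 0.878 | 0.883 |
| 2.0 | 8 | 0.652 | 0.681 |

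The difference is at most about 3 percentage points. The Wilcoxon test in its usual form drops zero changes, so there the two sets give the same result.

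**The case against.** **Dilution is not shown to have happened.** A reader might infer that pain-free participants did dilute the result. The documents do not support that: no baseline VAS or count of pain-free participants is reported, and section 1.0 says axial symptoms contribute to chronic pain in this disease, so the share could be small or nil. Lacking chronic back pain is also not the same as scoring 0, since other pain can be present and can improve. This stands. Dilution is conditional; the mismatch in step 1 is not.

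**Power is not the argument.** A reader might also infer that the smaller back-pain set is the more powerful one. That depends on assumptions the documents do not supply. Take d=2.0, s=2.0 and 8, 10 or 12 of 16 with back pain. Subset power is 68%, 80% and 88%. Pooled power is 65%, 79% and 88% if the rest do not change; 61%, 77% and 87% if their change has mean 0 and SD 0.5; and 78%, 85% and 90% if they improve by 0.25 on average (SD 0.5). The ordering reverses with a small change in assumption. The SD of 0.5 around a mean of 0 is also impossible for people at 0, who cannot improve. This objection stands in full.

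**Not selecting on a secondary symptom is legitimate.** Mobility is primary, and this is a pilot case series with no power calculation. That is fair as to recruitment. It does not license a conclusion about a population that was not selected or identified, and the pilot's declared purpose is to supply effect sizes and SDs.

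**It is too late to change data collection.** The document is written in the past tense, so a new entry question or a re-anchored VAS cannot be applied here. This stands and limits the fix to analysis, reporting and wording.

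**Conclusion.** The concern holds in this form: the pooled VAS change does not answer the stated pain objective. That follows from sections 2.0, 4.1, 4.2, 6.3, 7.2 and 7.4.2 alone and would remain even if every participant had some pain at baseline, because the site, recall window and chronicity are still not fixed.

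The numerical part is conditional on some participants having been pain-free and unchanged. Under that assumption the mean is 25% too small with 4 of 16 and 50% too small with 8 of 16 as an estimate for people with back pain. The loss in standardised effect further depends on the assumed d and SD. It distorts planning for a trial in chronic back pain; a later trial recruiting the same unselected mix could use the pooled figures, but only for overall pain. No claim is made that restricting the set materially improves power.

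This affects one secondary endpoint. The primary TUG analysis is untouched. It should still be corrected before the pain result is reported, because the correction is cheap and changes what can be concluded.

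**What to change.** **If chronic back pain status was recorded at entry and the VAS was administered for back pain:** report the pain endpoint in that subset, with all completers as supportive. Define the subset from the entry record, not from the baseline VAS; selecting on a high baseline score in a single-arm study would replace dilution with regression to the mean. State the definition of chronic and the site and recall period of the VAS as given to participants.

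**Otherwise:** rename the objective *overall pain intensity* and remove chronic back pain from the conclusions.

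**In either case:** report how many scored 0 at baseline and, where it was recorded, how many had chronic back pain, and say how a baseline of 0 is treated in the percentage calculation.

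**Cost:** a smaller n for this endpoint under the first route, a narrower claim under the second, and some SAP and report wording. An entry question on back pain and a back-anchored VAS with a fixed window belong in a future study.

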3.0 Study Design

This was a prospective, single-arm, observational case series conducted at a single clinical site (The Manual Therapy Clinic, Edinburgh, UK).

4.0 Eligibility Criteria

4.1 Inclusion Criteria

- Confirmed clinical diagnosis of Parkinson's Disease.
- Hoehn and Yahr Scale Stage 3 or below (indicating mild to moderate disability).
- Ability to walk independently for approximately 5 minutes (with or without walking poles; Zimmer frames excluded).
- Age 18 to 75 years.

4.2 Exclusion Criteria

Participants were excluded if they presented with any absolute contraindication to mechanical spinal mobilization, including:

- **Bone Pathology:** History of spinal malignancy, active spinal infection (e.g., tuberculosis), severe congenital defects, metabolic bone disease (e.g., severe osteomalacia), or currently healing fractures/dislocations.
- **Inflammatory Conditions:** Severe Rheumatoid Arthritis or other inflammatory arthritides.
- **Neurological Conditions (Non-PD):** Spinal cord compression, spinal cord damage, Cauda Equina syndrome.
- **Vascular Risks:** History of aortic dysfunction (e.g., aneurysm), severe haemophilia, or unmanaged bleeding disorders.

5.0 Study Intervention

Participants received therapy using the **BackHug** robotic spinal mobilization system.

- **Mechanism:** The device features 26 robotic therapeutic heads ('fingers') that deliver targeted deep-tissue pressure to the paraspinal muscles and intervertebral joints.
- **Regimen:** Participants attended four (4) sessions administered over a two-week period.
- **Duration:** Each session lasted approximately 40 minutes.
- **Settings:** Treatment intensity was personalized to user tolerance via the device's control app.

6.0 Outcome Measures

6.1 Functional Mobility (Primary Outcome)

- **Metric:** 3-Meter Timed Up and Go (TUG) Test.
- **Method:** Participants were timed (in seconds) as they rose from a chair, walked 3 meters, turned around, walked back, and sat down.
- **Timing:** Assessed at Baseline (Session 1 Pre-Therapy) and Post-Intervention (Session 4 Post-Therapy).

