6.2 Functional Strength (Secondary Outcome)

- **Metric:** 30-Second Sit-to-Stand (STS) Test.
- **Method:** The number of full stands completed in 30 seconds was recorded.
- **Timing:** Assessed at Baseline and Post-Intervention.

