7.0 Statistical Considerations

7.1 Sample Size

As a pilot observational case series, the sample size (N=16) was determined based on feasibility and the capacity of the single-center clinical facility. The objective was to generate effect size estimates and standard deviation data sufficient to power a future randomized controlled trial (RCT). No formal power calculation was performed prior to recruitment.

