7.2 Analysis Populations

- **Per-Protocol Population:** The primary analysis includes all participants who completed the full course of 4 therapy sessions and underwent both baseline and final assessments.
- **Safety Population:** Safety analysis includes all participants who received at least one session of therapy.

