7.3 Handling of Missing Data

Missing data points resulting from missed sessions or incomplete assessments were documented but excluded from the final efficacy calculation for that specific endpoint. No data imputation methods (e.g., Last Observation Carried Forward) were used. Analysis is based on observed cases only.

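### Session 4 is the only scheduled post-baseline TUG, so the change in any treated participant who did not reach it is unobserved, and the plan offers no way to account for that person.

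*Combined protocol and SAP*

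**What the plan says.** Protocol section 6.1 gives the TUG two time points: "Assessed at Baseline (Session 1 Pre-Therapy) and Post-Intervention (Session 4 Post-Therapy". Section 6.2 gives the 30-second sit-to-stand (STS) the same two-point pattern, "Assessed at Baseline and Post-Intervention", without naming a session. Pain (6.3) and sleep (6.4) are instead recorded repeatedly over the study.

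Section 5.0 describes the treatment: "Participants attended four (4) sessions administered over a two-week period".

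SAP section 7.2 defines the efficacy set: "The primary analysis includes all participants who completed the full course of 4 therapy sessions and underwent both baseline and final assessments". A wider set appears in the same section for safety only: "Safety analysis includes all participants who received at least one session of therapy". Section 7.3 deals with gaps: "Missing data points resulting from missed sessions or incomplete assessments were documented but excluded from the final efficacy calculation for that specific endpoint". It also rules out imputation.

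Section 7.1 gives the size and basis of the study: "the sample size (N=16) was determined based on feasibility and the capacity of the single-center clinical facility". It adds that the purpose is to supply effect sizes and standard deviations for powering a randomised trial.

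**The concern.** The final TUG is attached to a treatment event, the end of Session 4. Whether the primary outcome is measured therefore depends on adherence. Widening the analysis set does not cure this: it can bring back someone who was tested but excluded, but not a value that was never collected.

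The treatment is deep-tissue pressure on the spine, with intensity set to tolerance. It is plausible, though the documents do not show it, that people who stop do so because they tolerate it poorly or feel no benefit. If so, the observed mean change describes those who did well enough to finish. The study exists to pass an effect size to a randomised trial, and a value taken only from people who reached Session 4 could make that trial too small.

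**Working it through.** **1. The plan's own figure.** The only relevant figure is N=16. It cannot be reproduced, because section 7.1 gives no effect size, SD, power or dropout rate: "No formal power calculation was performed prior to recruitment". The check is therefore a reading of the schedule, followed by illustrative arithmetic.

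**2. Who has a final TUG, and who is analysed.**

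| Participant | Final TUG scheduled (6.1)? | In the efficacy set (7.2)? |
|---|---|---|
| Attended all four sessions, tested at both points | Yes | Yes |
| Missed Session 2 or 3, attended Session 4 | Yes | No, excluded by 7.2 |
| Stopped before Session 4, or missed it | No | No |

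The second row is a matter of analysis set and can be repaired from data in hand. The third row is the data-collection gap. Section 7.3 foresees missed sessions but responds by exclusion, without imputation or bounds.

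**3. Size of the possible overstatement.** Assumptions: all 16 were treated, and k of them have no final TUG. Let D be the mean change in those observed and d the mean change in those not observed.

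All-treated mean = [(16-k) × D + k × d] / 16.

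- If stoppers are unchanged (d = 0), D divided by the all-treated mean is 16/(16-k).
- If stoppers worsen by as much as the others improve (d = -D), it is 16/(16-2k).

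| k (assumed) | Share unobserved | 16/(16-k) | 16/(16-2k) |
|---|---|---|---|
| 0 | 0% | 1.00 | 1.00 |
| 1 | 6.25% | 16/15 = 1.07 | 16/14 = 1.14 |
| 3 | 18.75% | 16/13 = 1.23 | 16/10 = 1.60 |
| 4 | 25% | 16/12 = 1.33 | 16/8 = 2.00 |

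**4. A bound that does not fix the direction.** Suppose each unobserved change lies within 2 SD of the observed mean. The all-treated mean then lies within 2k/16 SD of it: 0.125 SD for k=1 and 0.50 SD for k=4. For scale, the sampling 95% half-width, t(0.975, m-1)/√m with m observed, is 0.53 SD for m=16 and 0.64 SD for m=12. At k=4 the uncertainty from unobserved values approaches the sampling uncertainty; at k=1 it is much smaller.

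**5. Chance that the problem arises.** With an assumed independent rate q of lacking a final TUG, the probability that at least one of 16 is affected is 1 - (1-q)^16: 28% at q=2%, 56% at 5% and 82% at 10%.

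**6. Consequence for the future trial.** At a fixed SD, the required sample size varies with 1/effect². A trial sized on the completer mean, when stoppers are unchanged, would have (15/16)² = 0.88 of the number needed at k=1 and (12/16)² = 0.56 at k=4. Holding the SD fixed is a simplification.

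**The case against.** The strongest reply is that the problem may never have occurred. Section 5.0 can be read as saying that everyone attended four sessions, and no document reports a stopper. If every treated participant had the Session 4 test, the observed and all-treated means are the same. This stands, and it makes the point conditional. It does not remove it: section 7.3 provides for missed sessions, section 7.2 separates those who completed from those merely treated, and neither gives a count.

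The study is also a small single-arm case series that openly declares a per-protocol, observed-case analysis. That limits how much weight the point carries, but the effect size is meant for use in sizing another trial.

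Some stronger readings are tempting, and the documents do not support them:

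- A reader might infer that no all-treated estimate could ever be built. It could, either because nobody is missing or through bounds or imputation under stated assumptions. What is lacking is any such provision in the plan, and any observed post-baseline TUG with which to check the assumptions.
- A reader might infer that nothing is known about those who stop. Pain and sleep are recorded throughout, and safety covers everyone treated. The gap concerns TUG and, apparently, STS.
- A reader might infer that STS is fixed to Session 4. Section 6.2 names no session; the link rests on a label shared with 6.1.
- A reader might infer that sessions slipped beyond two weeks and that final tests were late. No visit window is stated for the final test, but nothing shows that visits slipped.

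The stopping numbers and the worsening scenario in the working are assumptions. Personalised intensity may well have made stopping for intolerance less likely.

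**Conclusion.** The point holds in conditional form. Session 4 post-therapy is the only scheduled post-baseline TUG, and STS appears to follow the same pattern. If any treated participant did not reach Session 4, the planned result is an effect in those who did, and it cannot be extended to everyone treated without assumptions that the plan does not state. If nobody is missing, there is no bias.

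The size depends wholly on the unreported number missing and their unobserved change. With stoppers unchanged, the overstatement is modest for one person and about a third for four; it is larger if stoppers worsened. The matter should be addressed because the remedy is cheap and the estimate is intended for reuse. Confidence is medium, since the stopping rate is unknown.

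**What to change.** **If data collection has ended, as the past tense suggests:**

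- Report the number treated, the number with a final TUG and with a final STS, and the reasons for each missing value.
- Add an analysis of everyone with both values, whatever number of sessions they attended. This recovers anyone who missed Session 2 or 3 but was tested at Session 4.
- Add a sensitivity bound that counts treated participants without a final value as unchanged, and then as worse by a stated amount.
- Limit the TUG and STS conclusions, and the effect size passed to the randomised trial, to participants who reached Session 4.

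Sections 6.1 and 6.2 should not be rewritten to describe a visit that did not take place. The cost is a count, two short analyses and some wording.

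**If collection is still open:** keep the Session 4 post-therapy test as the primary value for those who reach it. For any treated participant who does not, do TUG and STS at the stopping visit or at the end of the two-week period within a stated window, and say in advance which value is used if both exist. The cost is one short repeat of existing tests for each person who stops. Some will not return, so the bound is still needed, and the mean change may become less favourable.

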6.2 Functional Strength (Secondary Outcome)

- **Metric:** 30-Second Sit-to-Stand (STS) Test.
- **Method:** The number of full stands completed in 30 seconds was recorded.
- **Timing:** Assessed at Baseline and Post-Intervention.

6.3 Pain Intensity (Secondary Outcome)

- **Metric:** Visual Analog Scale (VAS).

- **Scale:** 0 (No Pain) to 10 (Worst Possible Pain).
- **Timing:** Assessed longitudinally throughout the study.

6.4 Sleep Quality (Secondary Outcome)

- **Metric:** Self-Reported Likert Scale.
- **Scale:** 0 (Excellent) to 5 (Very Poor).
- **Timing:** Assessed longitudinally throughout the study.

STATISTICAL ANALYSIS PLAN (SAP)

7.0 Statistical Considerations

7.1 Sample Size

As a pilot observational case series, the sample size (N=16) was determined based on feasibility and the capacity of the single-center clinical facility. The objective was to generate effect size estimates and standard deviation data sufficient to power a future randomized controlled trial (RCT). No formal power calculation was performed prior to recruitment.

